6.1. Study Intervention(s) Administered

Details are provided in the intervention-specific sub-protocol(s).

6.2. Preparation, Handling, Storage, and Accountability

Instructions for the preparation of study intervention(s) are provided (e.g., reconstitution, mixing) in the applicable intervention-specific sub-protocol(s).

6.3. Measures to Minimize Bias: Randomization and Blinding

In addition to receiving SoC, all participants will be centrally assigned to randomized study interventions in the eCRF. When the participant has been deemed eligible for randomization, baseline information will be entered and then the participant will be randomised. Participants will be randomly assigned in an equal ratio between the intervention or comparator arms they are eligible for. Randomization will be computer-generated in permuted random-sized blocks with stratification. The stratification factors are shown in the table below. Randomization will be done at the baseline visit (day of study treatment initiation). For placebo-controlled interventions, the arm will not be revealed. Further details will be given in the intervention-specific protocol.

Table 6.3: Stratification factors of EU-SolidAct

EU-SolidAct Part A Moderate disease	EU-SolidAct Part B Severe disease

 - Centre - Need for oxygen at baseline (yes/no) 	
 - Centre - Previous entry in Part A (yes/no) - High flow oxygen or NIV vs mechanical ventilation/ECMO at baseline

Stratification by emerging treatment in SoC should be considered when these arise. Participants in EU-SolidAct Part A may undergo a second randomization at any point after being first randomized if they deteriorate and switch from moderate to severe/critical disease (EU-SolidAct Part B).

The second randomization will proceed as follow:

1. The informed consent form will cover both Part A and B. Thus, there will be no separate consent for the second randomization.

2. When a participant in Part A progresses and is eligible for Part B, the participant is screened against all intervention-specific protocols eligibility criteria. If the participant is eligible for at least one of the Part B interventions, the participant is randomised to one of the available interventions plus SoC or SoC alone.
3. The allocated treatment in Part A is continued unless instructed otherwise in the corresponding intervention-specific protocol, or by the discretion of the treating physician.

If one or more of the active drug treatments are not available at the hospital, opted out by the hospital or contraindicated for a specific participant, then this fact will be recorded via the web-based form prior to randomization; random allocation will then be between the remaining arms. If no treatments are available and suitable, the participant cannot be randomized and must be withdrawn from the trial.

This study could include both open-label and placebo-controlled interventions. In the case of open-label interventions, all investigators, site pharmacists, study nurses, sponsor safety staff and participants will be unmasked and aware of the treatment allocation throughout the study. However, they will be unaware of aggregate outcomes during the course of the study.

6.4. Study Intervention Compliance

This study is being conducted in hospitals. Treatment is administered at site and participants will receive study intervention directly from the investigator or designee, under medical supervision. The date and time of each dose administered in the clinic will be recorded in the source documents. Deviation(s) from the prescribed dosage regimen should be recorded via the web-based form. Intervention start and stop dates, including dates for intervention delays and/or dose reductions will also be recorded.

Further details are given in the intervention-specific sub-protocols.

6.5. Dose Modification

There are generally little clinical safety or pharmacokinetic data available for emerging diseases allowing modification in the recommended and approved dose of the study treatments for human.

Further details will be given in the intervention-specific sub-protocols.

6.6. Continued Access to Study Intervention after the End of the Study

Details given in the intervention-specific sub-protocol if applicable.

6.7. Treatment of Overdose

Details given in the intervention-specific sub-protocol if applicable.

6.8. Concomitant Therapy

Any medication or vaccine (including over the counter or prescription medicines and/or recreational drugs) at the time of enrolment or received during the study must be recorded along with:

- Reason for use
- Dates of administration including start and end dates
- Dosage information including dose and frequency

The national Coordinating Investigator should be contacted if there are any questions regarding concomitant or prior therapy.

If it is not feasible to collect all concomitant medication due to exhaustive medication lists, the priority should be to register at least changes in concomitant medication that could interfere with safety or efficacy of the tested drug, as specified in the intervention-specific sub-protocol.

Details on concomitant therapy including prohibited therapies, rescue medication, recording of vitamins and/or herbal supplements are given in the intervention-specific sub-protocol if applicable.

7. Discontinuation of Study Intervention and Participant Discontinuation/Withdrawal

Discontinuation of specific sites or of the study are detailed in Appendix 1.

7.1. Discontinuation of Study Intervention

In rare instances, it may be necessary for a participant to permanently discontinue the study intervention. If the study intervention is permanently discontinued, the participant will remain in the study to be evaluated at all follow-up visits scheduled for the study. See section 8 for data to be collected at the time of discontinuation of study intervention and follow-up and for any further evaluations that need to be completed. The date and reasons for stopping intervention will be clearly stated on the participant's electronic Case Report Form (eCRF) and source document.

Intervention-specific stopping criteria (e.g., liver biochemistry abnormalities, cardiac changes, pregnancy etc). are given in the intervention-specific sub-protocol if applicable.

7.2. Participant Discontinuation/Withdrawal from the Study

A participant may withdraw from the study at any time at his/her own request or may be withdrawn at any time at the discretion of the investigator for safety, behavioural, or compliance reasons. This is expected to be uncommon.

At the time of discontinuing from the study, if possible, an early discontinuation visit should be conducted. See section 8. for data to be collected at the time of study discontinuation and follow-up and for any further evaluations that need to be completed.

The participant will be permanently discontinued from the study intervention and the study at that time.

If the participant withdraws consent for disclosure of future information, the sponsor may retain and continue to use any data collected before such a withdrawal of consent.

If a participant withdraws from the study, he/she may request destruction of any samples taken and not tested, and the investigator must document this in the study site records.

There will be no replacements of withdrawn patients.

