7.3. Lost to Follow-Up

Lost to follow-up should not occur during the hospitalization period. However, after discharge from the hospital, participants could be lost to follow-up.

A participant will be considered lost to follow-up if he/she is unreachable for the study site per telephone directly to the patient or relatives (for at least two days), or by written correspondence, after hospital discharge and until end of study.

8. Study Assessments and Procedures

General instructions

Study procedures and their timing are summarized in Schedule of Assessments (SoA, section 1.2). Protocol waivers or exemptions are not allowed.

Safety concerns should be discussed with the sponsor or sponsor representative immediately upon notice, to determine if the participant should continue or discontinue the study intervention.

Adherence to the study design requirements, including those specified in the SoA, is essential and required for good study conduct.

- All assessments in level I (blue background colour in SoA table) are mandatory.
- Level II assessments (green background colour) include biobanking (necessary for virological outcomes) and are encouraged whenever possible.
- Level III assessments (grey background colour) include add-on studies on extended biobanking, imaging organ function and PROM. The accurate and complete description of what is to be measured and monitored will be defined by the units that run level III. This level will form the basis of sub-studies and is optional but should be performed according to common standardised protocols and standard operating procedures.

Screening assessments:

Screening for inclusion should be performed as soon as possible after hospitalisation. For participants progressing in Part A, screening for Part B should be done as soon as possible after progression. All screening evaluations must be completed and reviewed to confirm that potential participants meet all eligibility criteria. The investigator will maintain a screening log to record details of all participants screened and to confirm eligibility or record reasons for screening failure, as applicable.

Procedures conducted as part of the participant's routine clinical management (e.g., blood count) and obtained before signing of the informed consent form may be utilized for screening or baseline purposes provided the procedures meet the protocol-specified criteria and are performed the same day as screening or within 24 hours for baseline.

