- If readmitted, date of readmission and reason for readmission. Report as SAE.
- Review concomitant medication
- Adverse events by open-ended and non-leading verbal questioning of the participant
- Check that patient has answered online patient reported outcome measure (the Oslo COVID-19 QLQ-PW80)

Discharge visit/Early discontinuation visit

- Register WHO COVID-19 disease progression scale (0-10), see section 8.1.1.
- Review concomitant medication and adverse events
- If discharged, register whether the patient is discharged to home, home care facilities, other hospitals or other institutions or locations
- If early discontinuation, register reason for early discontinuation
- Participant withdrew consent to further participation
- Participant withdrawn by the investigator for safety, behavioural or compliance reasons including lost to follow-up
- Death
- For early discontinuation, answer online patient reported outcome measure (the Oslo COVID-19 QLQ-PW80).

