9.2. Analysis Sets

For the purposes of analysis, the following analysis sets are defined:

Participant Analysis Set	Description
Full analysis set	
 All randomized participants. Participants will be included in the analyses according to the planned randomized intervention.
Safety analysis set	
 All participants who are exposed to a study intervention. Participants will be analysed according to the intervention they actually received.

The full analysis set is used to analyse endpoints related to the efficacy objectives and the safety analysis set is used to analyse the endpoints and assessments related to safety.

The following data points sets are defined:

Defined Data Points Sets	Description
DPS1	
 All observed data will be included in the analysis set.

Defined Data Points Sets	Description
DPS2	
 For participants who discontinue study intervention and/or receive rescue therapy, post-discontinuation or post-rescue observations will not be included.

Full analysis set and DPS1 are used to estimate the primary endpoints and the secondary endpoints for secondary core objective.

Full analysis set and DPS2 are used to for sensitivity analyses.

Safety analysis set and DPS1 are used to present safety data.

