9.3.2. Primary endpoint(s) analysis

The primary endpoint for Part A is the occurrence of disease progression, defined as a progression of disease state from moderate (WHO scores 4-5) to severe/critical (WHO score 6-9) or death within 14 days, and the primary endpoint for Part B is the occurrence of death within 60 days. The Kaplan-Meier estimate will be used to estimate the disease progression rates. Kaplan-Meier curves will be plotted for the primary endpoints. We will calculate the Cochran-Mantel-Haenszel treatment difference and the 95% associated confidence interval in

the percentage of participants with disease progression (i.e., study intervention group response rate minus control group response rate) adjusted for the stratification factors of the randomization. The analyses may also be adjusted for other prognostic factors as sensitivity analyses. If the primary analysis adjusted for centre becomes unstable or non-identifiable due to small strata, adjustment by country will be done instead. The effect of study intervention will also be assessed using a time-to-event regression model with treatment group and adjustments for stratification factors.

The validity of the proportionality assumption will be evaluated and tested. Efforts to minimize lost to follow-up will be considerable. However, small amounts of missing data may occur. In such cases, participants without final outcome data will be censored at the date of last information. Sensitivity analyses will be conducted assuming all participants lost to follow-up progressed in both arms at time of censoring (worst case imputation), or none progressed and did not meet the primary endpoint (best case imputation). These sensitivity analyses will be fully defined in the statistical analysis plan (SAP).

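### Section 7.2 lets the investigator end a participant's follow-up for safety, behavioural or compliance reasons, which conflicts with section 7.1 and can informatively censor the primary endpoint

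*Protocol*

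**What the plan says.** Section 7.1 deals with permanent discontinuation of the study intervention. In that case "the participant will remain in the study to be evaluated at all follow-up visits scheduled for the study".

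Section 7.2 deals with leaving the study. Besides withdrawing at their own request, a participant "may be withdrawn at any time at the discretion of the investigator for safety, behavioural, or compliance reasons". The consequence is explicit: "The participant will be permanently discontinued from the study intervention and the study at that time". The section comments "This is expected to be uncommon" but gives no rate. It asks for an early discontinuation visit where possible and refers to section 8 for further follow-up. Withdrawal of consent to disclose future information has its own sentence.

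Section 8 (Discharge visit/Early discontinuation visit) lists one of the recordable reasons as "Participant withdrawn by the investigator for safety, behavioural or compliance reasons including lost to follow-up". For a withdrawn participant it describes that single visit and nothing later. The Schedule of Assessments puts end of study and early withdrawal in the same column.

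Section 8.6.1 does not oblige investigators to look actively for adverse events once participation has ended.

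On the analysis side, section 9.2 defines the full analysis set as "All randomized participants. Participants will be included in the analyses according to the planned randomized intervention". Section 9.3.2 states that "the primary endpoint for Part B is the occurrence of death within 60 days", and censors anyone without a final outcome at the date of last information.

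**The concern.** Safety and compliance problems are ordinary reasons to stop a study drug, and section 7.1 provides for that while keeping the participant under observation. Section 7.2 allows the same reasons to end observation altogether, at the investigator's discretion. Two participants with the same problem can therefore end up with different data: one has a known Day 60 outcome and the other is censored at the time of withdrawal.

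Kaplan-Meier and log-rank methods assume that censored participants carry the same later risk as those who remain. A participant removed for a safety reason plausibly does not. In open-label comparisons the investigator also knows the arm (section 6.3). In blinded ones, differences in tolerability can still make withdrawal differ between arms. The quantities at stake are the Part B mortality comparison, the Part A progression comparison, and the record of new SAEs after withdrawal. No statistical analysis plan can recover vital status that was never collected.

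**Working it through.** **1. What is still collected after each route**

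- Intervention stopped under 7.1: all scheduled visits, so vital status, readmission and adverse events to Day 91.
- Withdrawn by the investigator under 7.2: one early discontinuation visit if possible (WHO score, concomitant medication, adverse events, reason, questionnaire). No later vital status and no active search for new SAEs. SAEs and adverse events of special interest already reported are still followed under 8.6.3.

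The cross-reference from 7.2 to section 8 does not fill the gap, because section 8 has no later step for these participants.

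**2. The plan's own figures**

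Inputs from section 9.5.1, Part B: 15% against 10% mortality, two-sided 5%, 90% power.

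- HR = ln(0.90)/ln(0.85) = 0.648.
- Freedman: 231 events; 231/(0.15 + 0.10) = 924 per arm, as stated.
- Schoenfeld: 224 events, as stated.
- Dropout allowance: 950 − 924 = 26 per arm; 26/950 = 2.7%.

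**3. Illustration of the bias**

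The protocol gives no withdrawal rate, so what follows is assumption. Suppose 26 participants are withdrawn in one arm only, soon after randomization, and a share m of them die by Day 60. With such early censoring, the Kaplan-Meier estimate is close to the rate among the other 924:

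estimate = (true deaths − 26m)/924

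| True rate (deaths of 950) | m | Unseen deaths | Estimate | Understated by |
|---|---|---|---|---|
| 15% (142.5) | 0.30 | 7.8 | 134.7/924 = 14.6% | 0.4 points |
| 15% (142.5) | 0.50 | 13 | 129.5/924 = 14.0% | 1.0 points |
| 10% (95) | 0.30 | 7.8 | 87.2/924 = 9.4% | 0.6 points |
| 10% (95) | 0.50 | 13 | 82/924 = 8.9% | 1.1 points |

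With only 10 such withdrawals, m = 0.50 and a true rate of 10%, the estimate is 90/940 = 9.6%, understated by 0.4 points.

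If there is no true effect (15% in both arms), the standard error of the difference is √(2 × 0.15 × 0.85/950) = 0.0164. The 0.4 and 1.0 point biases then raise the two-sided rejection rate from 5% to 5.8% and 9.2%.

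**4. Would the planned sensitivity analyses show it?**

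*Withdrawal in one arm, true rate 10%, m = 0.50.* Best case is 82/950 = 8.6% and worst case is (82 + 26)/950 = 11.4%. The truth (10.0%) is bracketed, so the problem would be visible as a spread.

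*Equal numbers withdrawn, different prognosis.* Assume no true effect, 26 withdrawn in each arm, 50% of them dying on the intervention (13) and 15% on control (3.9).

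- Censored: 129.5/924 = 14.0% against 138.6/924 = 15.0%, a false difference of 1.0 point.
- Best case: 129.5/950 = 13.6% against 138.6/950 = 14.6%, difference 1.0.
- Worst case: 155.5/950 = 16.4% against 164.6/950 = 17.3%, difference 1.0 before rounding the rates (9.1/950).

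Because each imputation treats both arms alike, neither reveals the false difference in this setting.

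**The case against.** Several points on the other side have weight.

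- **Safety concerns are already directed to the drug.** Section 8 has them discussed with the sponsor to decide whether the intervention continues, and does not mention leaving the study. Section 7.2 expects withdrawal to be uncommon. This stands, and it makes frequent use of the 7.2 route less likely. It does not remove the permission, and it shows that 7.2 runs against the rest of the protocol.
- **SAE follow-up.** A reader might infer that safety follow-up is lost entirely. The documents do not support that. Section 8.6.3 follows reported SAEs and events of special interest to resolution, stabilization, explanation or loss to follow-up. Section 8.6.1 requires notification of later related SAEs, deaths included, that the investigator learns of. What lapses is vital status and the active search for new SAEs.
- **Loss to follow-up in 7.3.** A reader might infer that two days without telephone contact are enough to declare a participant lost. The sentence also covers contact with relatives, and it runs on "for at least two days), or by written correspondence, after hospital discharge and until end of study". It does not support that reading, and no change to it is proposed here.
- **Sensitivity analyses.** Worst-case and best-case imputation is planned and would expose a lopsided loss. That stands for one-arm withdrawal. It does not hold where numbers are similar and prognosis differs. The text also speaks only of participants lost to follow-up, so whether a deliberate withdrawal counts depends on the merged category in section 8. The primary estimate is exposed either way.
- **Size.** Giving the whole allowance to one arm and to this one reason is an upper-end scenario, since the 26 cover every cause of dropout. The only sub-protocol synopsis shown (baricitinib, section 10.8.1) is double-blind, so withdrawal there cannot follow known allocation. Both points stand.

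**Conclusion.** The conflict is real and lies in the current text. Section 7.2 allows discretionary removal from the study for reasons that section 7.1 treats as compatible with full follow-up, and this weakens an analysis of all randomized participants. Following the protocol as written can leave 60-day vital status, or Part A progression, unknown for a reason related to prognosis.

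The size cannot be derived from the protocol. Under one-arm, early withdrawal of up to 26 participants with 30% to 50% mortality, the understatement is about 0.4 to 1.1 points, at most roughly a fifth of the 5-point target difference (1.1/5 = 22%). With fewer withdrawals or similar prognosis across arms, it would be smaller. A reader might infer that a harmful drug would be made to look safe and effective. The figures do not show that. They show a modest, avoidable bias that the planned sensitivity analyses reveal only in part. The case for correcting the text rests on the contradiction and the low cost of repair.

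**What to change.** - **Section 7.2.** Reconcile it with 7.1. State that discontinuation initiated by the investigator for safety, behavioural or compliance reasons does not end follow-up. State that vital status, readmission and SAEs continue to be collected to Day 91, by the means already listed in footnote 8 of the Schedule of Assessments (telephone, patient records, primary caretaker, relatives), unless the participant or representative withdraws consent to further data collection.
- **Section 8, early discontinuation list.** Record loss to follow-up separately from withdrawal by the investigator, so that deliberate removal and failed contact can be told apart in the analysis.

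The cost is protocol and eCRF wording plus a few telephone or record checks of a kind the protocol already foresees. There are no extra visits, no extra participants and no change to the sample size. The rules on when the intervention itself is stopped are not affected.

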7.3. Lost to Follow-Up

Lost to follow-up should not occur during the hospitalization period. However, after discharge from the hospital, participants could be lost to follow-up.

A participant will be considered lost to follow-up if he/she is unreachable for the study site per telephone directly to the patient or relatives (for at least two days), or by written correspondence, after hospital discharge and until end of study.

8. Study Assessments and Procedures

General instructions

Study procedures and their timing are summarized in Schedule of Assessments (SoA, section 1.2). Protocol waivers or exemptions are not allowed.

Safety concerns should be discussed with the sponsor or sponsor representative immediately upon notice, to determine if the participant should continue or discontinue the study intervention.

Adherence to the study design requirements, including those specified in the SoA, is essential and required for good study conduct.

- All assessments in level I (blue background colour in SoA table) are mandatory.
- Level II assessments (green background colour) include biobanking (necessary for virological outcomes) and are encouraged whenever possible.
- Level III assessments (grey background colour) include add-on studies on extended biobanking, imaging organ function and PROM. The accurate and complete description of what is to be measured and monitored will be defined by the units that run level III. This level will form the basis of sub-studies and is optional but should be performed according to common standardised protocols and standard operating procedures.

Screening assessments:

Screening for inclusion should be performed as soon as possible after hospitalisation. For participants progressing in Part A, screening for Part B should be done as soon as possible after progression. All screening evaluations must be completed and reviewed to confirm that potential participants meet all eligibility criteria. The investigator will maintain a screening log to record details of all participants screened and to confirm eligibility or record reasons for screening failure, as applicable.

Procedures conducted as part of the participant's routine clinical management (e.g., blood count) and obtained before signing of the informed consent form may be utilized for screening or baseline purposes provided the procedures meet the protocol-specified criteria and are performed the same day as screening or within 24 hours for baseline.

The following assessments should be performed to determine eligibility requirements as specified in the inclusion and exclusion criteria:

- Register and review the positive SARS-CoV-2 test result
- Register and review SpO₂ measurement
- Register and review need for oxygen therapy, see section 8.1.2.
- Register and review prior and concomitant medication for allergies or contraindications to investigational medicinal products according to intervention-specific sub-protocol(s) eligibility criteria
- Register and review medical history for contraindications according to intervention-specific sub-protocol(s) eligibility criteria

- Register and review any other information according to intervention-specific sub-protocol(s) eligibility criteria

Once the patient is found to be eligible, go through the consent form with the patient and obtain informed consent.

Baseline procedures (Day 1):

After screening and obtaining informed consent, enter baseline data in the eCRF and randomize the patient (see section 6.3. for randomization procedure) as soon as possible after screening.

If participant is eligible for Part A include in Part A, if eligible for Part B include in Part B.

If not already collected as part of the intervention-specific sub-protocol assessment of eligibility criteria, collect the following information:

- Focused on medical history, including the following information:
 - Day of onset of COVID-19 symptoms
 - Day of hospitalization
 - History of chronic medical conditions and risk factors related to developing a severe COVID-19 disease: chronic pulmonary diseases (obstructive pulmonary disease, interstitial pulmonary disease, other), cardiovascular diseases (heart failure, coronary artery disease, other), kidney disease, liver disease, diabetes mellitus, hypertension, smoking, cancer, autoimmune diseases, immunodeficiency (HIV infection, primary immunodeficiency, other), neurological diseases
 - History of vaccination against COVID-19
 - History of prior infection
- Demographics (age, sex, country of birth)
- Register SoC details
- Register other concomitant medication than SoC if not already collected during screening. See details in section 6.8.
- Clinical Safety Laboratory Tests including pregnancy test for women of childbearing age, see section 8.3.5 and Appendix 2.
 - if more than 24 hours since screening, repeat blood samples for safety before first dose of study medication
 - If ferritin and procalcitonin are not routinely gathered at a site for clinical follow-up of the patient, these analyses should be prioritized at baseline, D8 and D15.
- Obtain vital signs including height in cm and weight in kg, see section 8.3.2.
- Collect data on oxygen therapy, see section 8.1.2.
- Register WHO COVID-19 disease progression scale (0-10), see section 8.1.1.
- Details of study treatment administration according to intervention-specific sub-protocol

Assessment until discharge:

Participants will be assessed daily for AE and SAE while hospitalized, see section 8.6.

- Note AE and SAE in the eCRF upon notice
- Safety concerns should be discussed with the sponsor to determine if the participant should continue or discontinue study intervention

The following clinical data will be noted in the eCRF obtained on Days 3, 5, 8 (± 1 day), and thereafter weekly (Day 15 ± 3 , Day 22 ± 3 , Day 29 ± 3 , etc.)

- Obtain vital signs, see section 8.3.2.
- Collect data on oxygen therapy, see section 8.1.2.
- Register WHO COVID-19 disease progression scale (0-10), see section 8.1.1.
- Review concomitant medication and note changes in the eCRF
- Draw and register blood samples for clinical safety laboratory tests (see section 8.3.5.)
 - If ferritin and procalcitonin are not routinely gathered at a site for clinical follow-up of the patient, these analyses should be prioritized at baseline, D8 and D15.

Details of study treatment adherence and administration will be given in the intervention-specific sub-protocol.

For level II of commitment:

Blood samples and naso/oropharyngeal swabs should be obtained at baseline (D1) before drug intervention starts. In addition, blood samples will be obtained on Days 3, 8, 15 and 22 (all ± 1 day), and naso/oropharyngeal swabs on Days 3, 8, 15 (all ± 1 day), as long as the patient is hospitalized.

Day 15 ± 3 , 29 ± 3 , 61 ± 7 :

If the patient has been discharged, the following information is gathered by phone or by reviewing the patient records:

- Alive or dead

If alive, recovery status

- Readmitted to hospital
- If readmitted, date of readmission and reason for readmission. Report as SAE.
- Review concomitant medication
- Adverse events by open-ended and non-leading verbal questioning of the participant

Follow-up assessment at Day 91 ± 14 :

A follow-up assessment by phone will be performed on Day 91 (± 14 days):

- Alive or dead

If alive, recovery status

- Readmitted to hospital
- If readmitted, date of readmission and reason for readmission. Report as SAE.
- Review concomitant medication
- Adverse events by open-ended and non-leading verbal questioning of the participant
- Check that patient has answered online patient reported outcome measure (the Oslo COVID-19 QLQ-PW80)

Discharge visit/Early discontinuation visit

- Register WHO COVID-19 disease progression scale (0-10), see section 8.1.1.
- Review concomitant medication and adverse events
- If discharged, register whether the patient is discharged to home, home care facilities, other hospitals or other institutions or locations
- If early discontinuation, register reason for early discontinuation
- Participant withdrew consent to further participation
- Participant withdrawn by the investigator for safety, behavioural or compliance reasons including lost to follow-up
- Death
- For early discontinuation, answer online patient reported outcome measure (the Oslo COVID-19 QLQ-PW80).

